7. DISCONTINUATION / WITHDRAWAL CRITERIA

7.1 Discontinuation of Study Drug

Subjects who wish to stop treatment for any reason may stop at any time during the study.

Reasons for discontinuing study drug may include:

- Unavoidable use of prohibited/excluded medications (see [Section 6.9](#))
- Administrative decision by the Investigator or the Sponsor
- Chronic or repeated subject noncompliance with the study drug dosing schedule (see [Section 6.5](#))
- Development of an AEs/SAEs/AESI at the discretion of the site Investigator, in consultation with the Medical Monitor. If the site Investigator deems the event urgent, then study drug should be held and consultation with the Medical Monitor regarding potential restart of study medication at the assigned or a reduced dose should be performed (see [Section 6.7](#))
- Unblinding of subject's study drug treatment assignment (see [Section 6.4](#))
- Subject becomes pregnant or wishes to discontinue birth control measures (see [Section 8.4.5](#))
- Any other reason that, in the opinion of the Investigator, precludes the subject's further participation in the trial

Subjects who permanently discontinue study drug will continue participation in the study, including participation in all remaining visits and assessments until the EoS visit. Subjects who have permanently discontinued study drug will not progress to the OLE study.

Details regarding subjects who discontinue study drug will be recorded on the appropriate page(s) of the eCRF. If a subject discontinues study drug because of an AE, the Investigator may be requested to schedule follow-up visits until the event has resolved or stabilized ([Section 4.6](#)).

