First investigational drug administration during TP1 will be selected from the “Investigational Drug Administration” CRF page for the Randomization Visit or vendor AiCure’s Dosing Diary data (selecting the first [Lorundrostat or Placebo] record following randomization) – the earlier available from each source.

Last investigational drug administration during TP1 will be selected from the “Investigational Drug Administration” CRF page for the Study Week 4 visit if the drug was administered at the Week 4 visit or, vendor AiCure’s Dosing Diary data (selecting the last [Lorundrostat or Placebo] record on or prior to Week 4 Study Visit Date, the latest available from each source.

First investigational drug administration during the Washout Period will be selected for the subjects who were dispensed placebo after the TP1 from the vendor AiCure’s Dosing Diary data (selecting the first [Placebo] record following Week 4 Visit. If that is not available, the first dose will be imputed as Week 4 Visit Date +1 day at 08:00 AM if the subject was dispensed placebo.

First investigational drug administration during TP2 will be selected from the “Investigational Drug Administration” CRF page for Study Week 8 visit if the administration occurred on Week 8 visit date or, vendor AiCure’s Dosing Diary data (selecting the first [Lorundrostat or Placebo] record on or after Week 8 visit [“Investigational Drug Administration” or “Date of Visit” CRF pages]) – the earlier available from each source. Only subjects who were dispensed drug on Week 8 visit record can have this information.

Last investigational drug administration during TP2. Only subjects with the First investigational dose administration in TP1 may have the last investigational drug administration in TP2. The last administration will be selected from the “Investigational Drug Administration” CRF page for Week12 / EoT visit (when study drug was administered at the visit) or vendor AiCure’s Dosing Diary data (selecting the last [Lorundrostat or Placebo] record following Week 12 visit [“Investigational Drug Administration” or “Date of Visit” CRF pages]) – the latest available from each source.

Safety Follow-up Period: All observations and measurements following End of Treatment Period 2 are considered safety Follow-up Period, including the EoS (Week 14/EoS) visit.

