This procedure will allocate measurements into Study weeks Baseline, Week 2, Week 4, Week 8, Week 10 and Week 12, as applicable. Subjects who do not participate in [REDACTED] may have Week 14/EoS visit. Week 14/EoS visit is Safety Follow-up. Subject is not on the study investigational medications during the Safety Follow-up Period. If there is an EoS Visit Date on the same date of the Study Visit Date, and the subject is on study medications, then the measurement maps into the Study Visit. All measurements that do not map into these visits will be listed but will not contribute to the summaries and analyses.

Next, for the analysis purposes, the measurements need to be organized into the cross-over design pattern, with two baselines corresponding to Study Week 0 and 8 and two treatment visits (Treatment Visit 2 and 4). This is in addition to the above windowing. The ADaM level data set will have data organized both by Study flow (above) and the data organized by Cross-Over design flow.

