6.3.4 Exposure and Adherence

The proportion of subjects who permanently discontinued blinded investigational drug, overall and by reasons for discontinuation, will be summarized overall and by Treatment Group within Randomized Sequence.

The proportion of subjects who experienced at least one temporary holding of blinded investigational drug, overall and by reasons for holding, will be summarized by treatment arm. Descriptive statistics of the duration of exposure to investigational drug in total and adjusted for temporary holds will be summarized by the treatment arm. Treatment duration, calculated as the number of days the subject received randomized investigational drug will be calculated as the date of the last dose minus the date of the first randomized dose + 1. The duration will be adjusted for temporary holds by subtracting days the investigational drug was temporarily held.

Treatment adherence will be defined by the treatment adherence ratio: the number of doses taken by the subject divided by the number of doses assigned.

Adjusted treatment adherence will be defined by the treatment adherence ratio: the number of doses taken by the subject divided by the number of doses assigned adjusting for the treatment holds.

A listing of the exposure and adherence parameters will be provided, including reasons for modification, if they occur.

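### SAP 5.2 looks for the last TP2 dose after the Week 12 visit, so subjects who stop drug early in TP2, withdraw, or are not dosed in clinic at Week 12 get no last-dose date

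*SAP*

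**What the plan says.** SAP 5.2 (Period and date definitions) gives the last TP2 dose two sources and takes the later. One is the dosing page for the Week 12/EoT visit, used only when drug was given at that visit. The other is the dosing diary, "selecting the last [Lorundrostat or Placebo] record following Week 12 visit". Eligibility for such a date is set by this sentence: "Only subjects with the First investigational dose administration in TP1 may have the last investigational drug administration in TP2".

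The matching TP1 rule searches the diary in the other direction, "selecting the last [Lorundrostat or Placebo] record on or prior to Week 4 Study Visit Date". The rule for the first TP2 dose has its own condition, tied to Week 8: "Only subjects who were dispensed drug on Week 8 visit record can have this information".

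Three other places bear on the point:

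- Protocol 7.1: "Subjects who permanently discontinue study drug will continue participation in the study". Early stoppers can therefore attend Week 12 without being dosed there.
- SAP 5.5.1: "Subject is not on the study investigational medications during the Safety Follow-up Period". No scheduled TP2 dose should therefore exist after the end of TP2.
- SAP 6.3.4: treatment duration is "calculated as the date of the last dose minus the date of the first randomized dose + 1", and it is summarised by treatment arm.

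**The concern.** The diary rule searches the part of the record where no TP2 dose is expected and ignores the four weeks in which TP2 doses are taken. It works only for subjects whose last dose was given in clinic at Week 12. It fails for subjects with short TP2 exposure, who are the ones an exposure summary needs to show. Permanent discontinuation for adverse events or laboratory findings is foreseen in the SAP as an intercurrent event (Table 5), so such subjects are expected.

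Three things depend on the date: TP2 treatment duration in SAP 6.3.4; the SAP 6.6.6 rule that medications started after the last dose are not concomitant; and, where there is no Week 12/EoT visit, the end of TP2 in SAP 5.2. SAP 5.2 gives an imputation for a missing first washout dose but none for a missing last TP2 dose.

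**Working it through.** The plan states no figure to reproduce. The check is to apply the rule as written to typical subjects and compare it with the SAP's own TP1 rule carried over to TP2.

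**Inputs.** Nominal days with the first TP1 dose as day 1: Week 8 = day 57, Week 12 = day 85. Duration within TP2 = last dose day − first dose day + 1 (SAP 6.3.4, read as applied within each period, which a display by arm requires). The mirrored rule uses diary records from the first TP2 dose up to the Week 12 visit, or the in-clinic Week 12 dose if later.

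| Subject | SAP rule as written | TP1 rule mirrored |
|---|---|---|
| Completer, dosed in clinic at Week 12 | day 85; 85 − 57 + 1 = 29 days | day 85; 29 days |
| Completer, dosed at home on the Week 12 morning, not in clinic | no date | day 85; 29 days |
| Stops after 10 TP2 days, attends Week 12 | no date | day 66; 66 − 57 + 1 = 10 days |
| Stops after 10 TP2 days, withdraws, no Week 12 visit | no date (no visit to anchor on) | day 66; 10 days |
| Dosed in TP1 only | no date (correct) | no date (correct) |

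**Can *following* be read as *up to*?** No. The same section uses the word for records after randomization and after the Week 4 visit.

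**Does the TP1 condition cause the loss?** No. Every TP2-dosed subject in the table was also dosed in TP1, so the condition excludes none of them. The TP1-only subject passes it but has no qualifying record, so still gets no date. The missing dates come from the direction of the diary search.

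**Size.** The documents do not say how many subjects will stop in TP2. Assume 60 subjects, 6 stopping after 10 days of TP2 (3 from each sequence), 28 days for everyone else, and TP1 complete. Each arm combines TP1 of one sequence with TP2 of the other, giving 60 subject-periods per arm.

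- True arm mean: (57 × 28 + 3 × 10) / 60 = 1,626 / 60 = 27.1 days.
- Reported arm mean, with the 3 missing: (57 × 28) / 57 = 28.0 days.
- Overstatement: 0.9 day.

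In general, with k stoppers split evenly, the overstatement per arm is (k/2) × 18 / 60. For k = 3 to 9 (5% to 15% of 60) it is 0.45 to 1.35 days. If TP2 is shown on its own, it is k × 18 / 60, or 0.9 to 2.7 days. The short durations also drop out of the minimum and possibly the lower quartile.

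**The case against.** The strongest reply is that this is a drafting slip. The adjacent TP1 rule shows the likely intent, a programmer would notice the empty dates, and early stoppers still appear in the discontinuation summary and exposure listing. That is fair as to consequence. But SAP 1.1 presents the SAP as the definitive plan, and a repair made in programming would leave the choice of records undocumented.

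A reader might infer wider damage. The documents do not support it:

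- **End of TP2 and the TEAE window.** SAP 5.2 ends TP2 at the later of the last dose and the Week 12/EoT visit. When that visit exists it fixes the start of Safety Follow-up, and the 14-day window in SAP 6.6.2.2 holds. Only withdrawers without the visit are exposed.
- **Rescue window.** SAP 6.6.6 lets it run to the Week 12 AOBP assessment if that is later, and censoring is at Week 12/EoT.
- **Pharmacokinetics.** SAP 6.5 is redacted and SAP 5.5.2 uses actual dates and times, so an effect on the PK dosing history cannot be shown.
- **Completers.** The Schedule of Assessments plans in-clinic dosing at Week 12, which gives the right date. A diary entry after the visit could move it later, but no such entries are documented. A tablet really taken then would be the true last dose.
- **Primary analysis and adherence.** The primary model uses planned treatment and the adherence ratio uses dose counts. Neither needs this date.

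It is also tempting to compare a pooled TP2 mean of (54 × 28 + 6 × 10) / 60 = 26.2 days with 28.0. SAP 6.3.4 summarises by arm across both periods, and there the difference is half as large.

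**Conclusion.** As written, the rule gives no last TP2 dose to subjects who stop early in TP2, withdraw before Week 12, or are not dosed in clinic at Week 12. For them TP2 duration is missing, rather than numerically wrong, and the cut-off between concomitant and post-treatment medication is undefined. For withdrawers with no Week 12/EoT visit, the end of TP2 is undefined too. Arm-level mean exposure is overstated by about 0.9 day under the assumed 6 stoppers at 10 days; the size scales with a count that the documents do not give.

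A reader might infer that requiring a first dose in TP1 is part of the cause. It is not. TP2 is evidently meant, but this is a separate wording error that removes no date. No efficacy conclusion is at risk. The rule should still be corrected, because it misstates exposure for the subjects with the shortest exposure and the correction is cheap.

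**What to change.** In SAP 5.2, redefine the last TP2 dose as the later of:

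- the last diary record on or after the first TP2 dose and on or before the Week 12/EoT visit, or the early-withdrawal visit if there is no Week 12 visit;
- the in-clinic Week 12 dose.

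The lower bound is needed so that a subject with no TP2 diary entries does not pick up a washout placebo record. When neither source gives a date, use the study drug stop date, which the compliance text in Protocol section 6 already requires sites to record. Change the eligibility condition to a first dose in TP2. List any diary record dated after the visit, so that a dose really taken then stays visible.

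The cost is a short SAP wording change and a programming update, with no new data collection.

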Subjects who were [REDACTED] may have Safety Follow up period after the Run-In. Subjects who have discontinued the study early may have an EoS prior to Study Week 14.

Derivations

Numerical results for the laboratory results that have observations reported as “<xx” and “>xx” will be calculated as follows. The laboratory data file contains numerical result precision variables for the results in conventional (CNVRESNP, Conventional Numeric Results Precision) and the SI units (SIRESNP, SI Numeric Results Precision). The numerical result will be calculated by subtracting (for the results with “<”) or adding (for the results with “>”) the (CNVRESNP-8) for the conventional units and (SIRESNP-8) for the SI units. By a way of example, the result that is <3.4 in the SI units and the SIRESNP=8.1, the numerical result will be calculated as: [REDACTED]

Derivation of Automated Office Blood Pressure (AOBP) parameters: There are 12 derived AOBP parameters five for the measurements obtained in the sitting position, 5 for the measurements obtained in the standing position, and two comparing standing and sitting SBP and DBP. The parameters are derived from the raw AOBP measurements according to the specifications provided in Sponsor document titled “Derivation of AOBP parameters” from 07 Nov 2024.

The number of antihypertensive (AHT) medications will be derived as follows. The AHT medications will be selected from the Concomitant Medications coded by using the Anatomical Therapeutic Chemical (ATC) Classification 2nd level code. The following ATC 2nd level are considered AHT medications (Table 1). For combination medications each medication counts as a separate medication. For example, a combination of beta blocking agent and a thiazide diuretic (ATC4 Code “C07B”) counts as 2 medications.

Table 1 Anatomical Therapeutic Chemical codes for antihypertensive medications

ATC 2 nd Level Code	Description
C02	Antihypertensives
C03	Diuretics
C07	Beta Blocking Agents
C08	Calcium Channel Blockers
C09	Agents Acting on the Renin-Angiotensin System

Corrected Serum Sodium will be calculated as follows. If serum glucose [REDACTED] then corrected sodium = Measured sodium + [REDACTED] Serum glucose - 100); otherwise Corrected Sodium = Measured sodium; where sodium is in mmol/L and glucose in mg/dL. Corrected sodium will be rounded to the nearest integer.

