Body Mass Index (BMI): weight (kg) / height(m)². Round to one decimal place precision (xx.x). Height is obtained only at the screening and it will be used for all BMI derivations.

eGFR (Cystatin C) (PARAMCD = "GFRE2012") will be calculated using the CKD-EPI Cystatin C Equation (2012) available at: [CKD-EPI Cystatin C Equation \(2012\) | National Kidney Foundation](#).

$$eGFR = \frac{1}{\left(\text{Scys} / \left(0.499 \times \max(\text{Scys}, 1) \right) - 1 \right)^{2.7396} \times \text{Age} \times 0.932} \text{ [if female]}$$
where,

eGFR (estimated glomerular filtration rate) = mL/min/1.73m²

Scys (standardized serum cystatin C) = mg/L,

min = indicates the minimum of Scys/1.73m²

max = indicates the maximum of Scys/1.73m²

age = years

Round to the nearest integer.

ARR (Aldosterone to Renin Ratio) (PARAMCD = "ARR") as Serum Aldosterone (ng/dL) / Renin (ng/mL/hr). Round to 2 decimal places precision (x.xx).

Urine Albumin-to-Creatinine Ratio (UACR1) as (Spot Urine Albumin (mg/dL) to Spot Urine Creatinine (mg/dL)). The result's PARAMCD="UACR" and PARAM is "Urine Albumin to Creatinine Ratio (mg/g) (Spot Urine)". Round to two decimal places precision (x.xx). This parameter is already calculated in the original central laboratory data but is expressed as g/g. It needs to be multiplied by 1000 to obtain the result in mg/g. No new calculation should occur except for the multiplication by 1000.

Urine Albumin-to-Creatinine Ratio (UACR2) as 24-h Urine Albumin (mg/day) to 24-h Urine Creatinine (mg/day)). The result's PARAMCD="UACR" and PARAM is "Urine Albumin to Creatinine Ratio (mg/g) (24-h Urine)". Round to two decimal places precision (x.xx).

Urine Protein-to-Creatinine Ratio (UPCR1) as (Spot Urine Protein (mg/dL) to Spot Urine Creatinine (mg/dL)). The result's PARAMCD="UPCR1" and PARAM is "Urine Protein to Creatinine Ratio (mg/g) (Spot Urine)". Round to two decimal places precision (x.xx). This parameter is already calculated in the original central laboratory data but is expressed as g/g. It needs to be multiplied by 1000 to obtain the result in mg/g. No new calculation should occur except for the multiplication by 1000.

Urine Protein-to-Creatinine Ratio (UPCR2) as 24-h Urine Protein (mg/day) to 24-h Urine Creatinine (mg/day)). The result's PARAMCD="UPCR2" and PARAM is "Urine Protein to Creatinine Ratio (mg/g) (24-h Urine)". Round to two decimal places precision (x.xx).

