Urinary Aldosterone-to-Creatinine Ratio (24-h Urine) is calculated as a ratio of urine aldosterone excretion (ng) and the simultaneous urine creatinine excretion (mg). The PARAMCD will be "U24ALDCR" and the PARAM "24-h Urine Aldosterone (ng) to Creatinine (mg) Ratio". Round to two decimal places precision (x.xx).

Identifying ARB and ACEi medications will be as follows. The ARB and ACEi medications will be selected from the Concomitant Medications coded by using the Anatomical Therapeutic Chemical (ATC) Classification 3rd level code. The following ATC 3rd level are considered ARB and ACEi medications (Table 2).

Table 2 Anatomical Therapeutic Chemical codes for ACEi and ARB medications

Medications	ATC 3 rd Level Code	Description
ARB	C09C	Angiotensin II receptor blockers (ARBs), plain
ARB	C09D	Angiotensin II receptor blockers (ARBs), combinations
ACEi	C09A	ACE inhibitors, plain
ACEi	C09D	ACE inhibitors, combinations

Identifying SGLT2i medications will be as follows. The SGLT2i medications will be selected from the Concomitant Medications coded by using the Anatomical Therapeutic Chemical (ATC) Classification 4th level code. The following ATC 4th level will be considered for SGLT2i medications (Table 3).

Table 3 Anatomical Therapeutic Chemical codes for SGLT2i medications

ATC 4 th Level Code	Description
A10BK	Sodium-glucose co-transporter 2 (SGLT2) inhibitors

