6.6.3.3 Additional summaries

The following laboratory tests will be in addition summarized using geometric mean, geometric standard error and two-sided 90% geometric confidence intervals. Only the analysis value will be summarized, by Treatment Period and Treatment Group within the period and by Treatment Group in Total for each analysis visit.

Table 9 Laboratory tests summarized by geometric means

Laboratory Test Name
Urine Albumin Excretion Rate
Serum Aldosterone
Serum Aldosterone / Renin Ratio
Urine Aldosterone Excretion Rate
Plasma Renin Activity
24-h Urine Aldosterone to Creatinine Ratio
Urine Albumin to Creatinine Ratio (both spot urine and 24-h urine)
Urine Protein Excretion Rate
Urine Albumin
Urine Protein to Creatinine Ratio (both spot and 24-h urine)
Urine Protein

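### Several derivation rules in SAP 5.2 give wrong values if followed as written, chiefly the 24-hour UACR and UPCR, which come out 1000 times too small for their mg/g label

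*SAP*

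**What the plan says.** All five rules are in SAP 5.2 (Data Conventions).

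- **24-hour ratios.** The SAP gives "Urine Albumin-to-Creatinine Ratio (UACR2) as 24-h Urine Albumin (mg/day) to 24-h Urine Creatinine (mg/day") and labels it "Urine Albumin to Creatinine Ratio (mg/g) (24-h Urine"). It gives "Urine Protein-to-Creatinine Ratio (UPCR2) as 24-h Urine Protein (mg/day) to 24-h Urine Creatinine (mg/day"), also labelled mg/g. Both are rounded to two decimals. For the two spot ratios, which the central laboratory supplies in g/g, the SAP adds: "It needs to be multiplied by 1000 to obtain the result in mg/g". The 24-hour ratios have no such sentence.
- **Parameter codes.** Spot and 24-hour UACR both have PARAMCD `UACR`. The protein ratios have separate codes, `UPCR1` and `UPCR2`.
- **Results reported as `<` or `>` a limit.** The numeric value is the limit minus or plus "the (CNVRESNP-8) for the conventional units and (SIRESNP-8) for the SI units". The one example is <3.4 with precision code 8.1; its answer is blacked out.
- **Last dose in Treatment Period 2 (TP2).** It comes from the Week 12/EoT dosing page, if a dose was given at that visit, or from the diary by "selecting the last [Lorundrostat or Placebo] record following Week 12 visit". The parallel rule for Treatment Period 1 (TP1) takes diary records up to and including the Week 4 visit.
- **Table 2.** C09D is listed for ARB combinations and again for "ACE inhibitors, combinations".

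**The concern.** The SAP calls itself the definitive analysis plan (Section 1.1), so a programmer may fairly apply these rules literally.

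The 24-hour UACR matters more than its place in a derivation list suggests. In the schedule of assessments, first morning void is collected at Screening and Weeks 0, 4 and 12. The 24-hour collection is also made at Week 8, which is the TP2 baseline. It is therefore the only scheduled albuminuria ratio with a baseline in both periods of the crossover.

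SAP 6.6.3.3 (Table 9) summarises spot and 24-hour UACR and UPCR, serum aldosterone, plasma renin activity and "Serum Aldosterone / Renin Ratio" by geometric mean. A geometric mean needs strictly positive values, so a rule that can return zero or less is a problem there. The last-dose date feeds treatment duration (6.3.4) and the cut-off for concomitant medication (6.6.6).

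**Working it through.** **1. Units of the 24-hour ratios.** Inputs: the SAP 5.2 formulas and labels, and the entry range of 200 to 5000 mg/g (protocol 5.1). The 1500 mg/day creatinine excretion is illustrative.

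- The SAP's own factor: (mg/dL)/(mg/dL) = g/g, and 1 g/g = 1000 mg/g. The spot instruction is reproduced.
- The same algebra for 24-hour urine: (mg/day)/(mg/day) = g/g, so the same factor is needed.
- 300/1500 = 0.20 as written; 0.20 × 1000 = 200 mg/g.
- 7500/1500 = 5.00 as written; 5.00 × 1000 = 5000 mg/g.
- Rounding g/g to two decimals gives steps of 0.01 × 1000 = 10 mg/g. True values of 196 and 204 mg/g both become 0.20. The largest rounding error is 5 mg/g, which is 5/200 = 2.5% at the bottom of the entry range.

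**2. Parameter code.** A selection on PARAMCD = `UACR` returns spot values in mg/g together with 24-hour values that, under rule 1 as written, are 1000 times smaller. Only the PARAM text separates them.

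**3. Censored results.** I read the precision code as width.decimals, as the example implies. Code 8.k then shifts the limit by k/10. One unit in the last decimal place is 10^-k. The two agree only at k = 1. All limits below except 3.4 with code 8.1 are hypothetical.

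| Reported | Code | SAP rule | Limit minus one last-place unit |
|---|---|---|---|
| <3.4 (SAP example) | 8.1 | 3.3 | 3.3 |
| <3.40 | 8.2 | 3.20 | 3.39 |
| <0.10 | 8.2 | -0.10 | 0.09 |
| <0.1 | 8.1 | 0 | 0 |
| <5 | 8.0 | 5 | 4 |

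The SAP rule gives a negative value when the limit is below k/10 (below 0.2 for code 8.2) and zero when the limit equals k/10. The fourth row shows that a step of 10^-k alone is not enough: a positive floor is needed too.

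**4. Last TP2 dose.** Take a subject who stops drug at Week 9 and stays for the remaining visits, as protocol 7.1 expects. No dose is given at Week 12, so the dosing page supplies no date. No diary dose follows Week 12, so the diary supplies none either. Treatment duration is last dose minus first dose plus 1 and cannot be computed from this rule.

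**5. Table 2.** One third-level code appears under two drug classes. The code alone cannot place a combination product in one of them.

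**The case against.** The best defence of the 24-hour ratios is that the target unit is stated. The label says mg/g, and the ×1000 sentence for the spot ratios can be read as an import instruction for a value that arrives in g/g. Results of 0.20 to 5.00 would stand out: all fall in the lowest UACR category of SAP 6.3.2 (below 30 mg/g), against entry at 200 mg/g or more. A constant factor also cancels in a ratio to baseline, apart from rounding. This makes it likely that the error would be noticed. It does not make the written rule right, and the rounding loss remains if conversion comes after rounding.

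The other defences narrow the point:

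- The two UACR parameters differ in PARAM text, and Table 9 asks for both, so pooling needs a selection on code alone.
- The documents show no precision code other than 8.1 and no reporting limit for any analyte. Table 9 is additional to the ordinary laboratory summaries.
- The TP2 wording is evidently a slip beside the correct TP1 wording. The end of TP2 and the rescue-medication window each take the later of two dates, so they are largely protected. No study drug is dispensed at Week 12, so dosing recorded after it is unlikely. The protocol has drug stop dates recorded, though the SAP rule does not use them.
- No visible analysis separates ACE inhibitors from ARBs.

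A reader might infer that negative aldosterone values would gather in the lorundrostat periods and bias the comparison, since the drug lowers aldosterone. That would require aldosterone to be censored at a limit and precision that trigger the fault, and the documents show neither. A reader might also take both 24-hour ratios to share the spot UACR code; 24-hour UPCR has its own.

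**Conclusion.** The rules are wrong as written, with unequal weight.

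- **Certain from the text:** both 24-hour ratios are low by a factor of 1000 against their label, with a resolution of 10 mg/g; the UACR code is duplicated; the TP2 diary search points the wrong way; C09D is duplicated.
- **Certain as arithmetic, conditional in effect:** the step for censored results is right only at one decimal. Whether any value becomes zero or negative depends on codes and limits that the documents do not give.
- **Limited consequence:** the missing last-dose date affects mainly the exposure summaries, and the C09D duplicate affects no visible analysis.

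It would be tempting to conclude that the trial's main result is at risk. It is not: the primary AOBP SBP endpoint, its model, its missing-data handling and the sample size use none of these rules. The exploratory endpoints and subgroup analyses are blacked out, so an effect on a tested albuminuria endpoint can be neither shown nor excluded. This is a should-fix.

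**What to change.** In SAP 5.2:

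1. For UACR2 and UPCR2, multiply the ratio by 1000 and round afterwards.
2. Give spot and 24-hour UACR separate codes, such as `UACR1` and `UACR2`, to match the protein ratios.
3. For results reported as `<` or `>`, subtract or add 10^-d, where d is the number of decimals, and state a positive floor for `<` results.
4. Take the last TP2 dose as the last record from the first TP2 dose up to and including Week 12/EoT.
5. Check the two C09D rows of Table 2 against the ATC index and correct the duplicate.

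The cost is SAP wording and programming. No new data are needed, and the design and the primary analysis do not change.

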5.1 Inclusion Criteria

Subjects eligible for inclusion in this study must meet **all** the following criteria:

1. Written informed consent, obtained before any study-related assessment is performed
2. At least 18 years of age at the time of signing the informed consent form (ICF)
3. At Screening, UACR of 200-5000 mg/g, inclusive, in first morning urine void
4. At Screening, eGFR of ≥ 30 mL/min/1.73 m²
5. At Screening, AOBP SBP of 135-180 mmHg, inclusive
6. At Randomization, AOBP SBP of 135-180 mmHg, inclusive
7. On a stable treatment with an ACEi or ARB for at least 4 weeks prior to Screening
8. At Screening, serum cortisol (morning measurement, blood draw as close to 8 AM as possible between 3 and 22 µg/dL, inclusive)
9. At Screening, body mass index (BMI) of ≥ 18 kg/m²
10. Fertile male subjects and female subjects of childbearing potential must agree to use an acceptable method of contraception ([Appendix 12.4](#)) from the Screening Visit to 28 days after the last dose of study drug in each study part
11. Willing and able to comply with the study instructions and attend all scheduled study visits, and are capable of providing informed consent

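### SAP Table 2 gives ATC code C09D to both ARB combinations and ACE inhibitor combinations, so no product under that code can be assigned to a single class

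*SAP*

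**What the plan says.** SAP 5.2 (Data Conventions) takes ARB and ACEi medications from the coded concomitant medications by ATC 3rd-level code. The operative sentence is "The following ATC 3rd level are considered ARB and ACEi medications (Table 2", and the table that follows has four rows. Two of them cover plain products and have separate codes, C09C for ARBs and C09A for ACE inhibitors. The other two cover combinations. On the ARB side the entry reads "C09D Angiotensin II receptor blockers (ARBs), combinations". On the ACEi side the code is the same one again, and the entry reads "C09D ACE inhibitors, combinations".

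The visible text offers no 4th-level code, preferred term or ingredient rule to tell the two combination rows apart. SAP 5.1 names the medication dictionary as WHO Drug, version Global B3.

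Background therapy with one of the two classes is part of the trial's definition. Protocol 5.1, inclusion criterion 7, requires subjects to be "On a stable treatment with an ACEi or ARB for at least 4 weeks prior to Screening", and the primary estimand in SAP 6.4.1.2 describes population and treatment in the same terms.

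**The concern.** A lookup keyed on code alone needs each code to point to one class, and C09D points to two. Combination tablets are not a remote case here: SAP 5.2 gives its own rule for counting their components as separate antihypertensives.

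What is at stake is the description of background therapy. A subject on one combination tablet could be shown as taking both an ARB and an ACE inhibitor. Depending on where the dictionary places the product, the subject could instead be shown as taking neither. A programmer could repair this by drug name, but that would be an undocumented departure from the SAP.

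**Working it through.** No figure in the plan needs to be reproduced. The check applies Table 2 literally and then asks where the result is used.

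**Step 1: the lookup as written.** The inputs are the four rows of SAP Table 2.

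| Code | Class or classes assigned |
|---|---|
| C09C | ARB |
| C09A | ACEi |
| C09D | ARB and ACEi |

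Four rows yield three distinct codes. No code maps to ACEi combinations alone, and none maps to ARB combinations alone.

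**Step 2: what happens to combination products.** The documents do not show how the dictionary codes them, so I take the possibilities in turn. "Elsewhere" below means a code that Table 2 does not list.

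| Where the dictionary places them | ARB combinations | ACEi combinations |
|---|---|---|
| C09D holds ARB combinations; ACEi combinations elsewhere | both flags | no flag |
| C09D holds ACEi combinations; ARB combinations elsewhere | no flag | both flags |
| C09D holds both groups | both flags | both flags |

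In all three cases a C09D product is flagged as both classes. The missing flag arises only in the first two.

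**Step 3: the either-class question.** For the question of whether a subject takes an ACE inhibitor or an ARB, a C09D record gives the correct answer, yes. That answer fails only for a combination group filed elsewhere, and only when the subject has no other qualifying record.

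**Step 4: where the split is used in the visible plan.**

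- Primary model (SAP 6.4.1.4): the terms are baseline difference, sequence, period, baseline difference by period, and treatment. There is no ARB or ACEi term.
- Number of antihypertensives (SAP 5.2, Table 1): uses 2nd-level C09 as a whole.
- Concomitant medication summary (SAP 6.6.6): uses ATC level 2.
- Analysis sets (SAP 4.1): depend on steps such as consent, randomization, dosing and PK sampling, not on a medication flag.
- Baseline characteristics (SAP 6.3.2): include antihypertensive class, without a clear ATC level and without naming Table 2.
- Rescue medication (SAP 6.6.6): excludes same-class replacement, but does not say that Table 2 decides class.
- Subgroups: SAP 6.4.1.6 is redacted and SAP 6.2.6 is not in the text supplied, so use there can be neither confirmed nor ruled out.

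**Step 5: after correction.** Giving one combination group its own code (a placeholder here, since the documents do not supply it) produces four rows and four distinct codes, each mapping to one class. The double flag disappears.

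**The case against.** The strongest reply is that nothing visible depends on the split. As step 4 shows, no model, analysis set or named table is tied to it, and the one place most likely to use it, the subgroup text, cannot be read. This stands, and it sets the weight of the point.

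A reader might infer that affected subjects would count as failing inclusion criterion 7. The documents do not support that. Eligibility is confirmed at the site during screening, not by a later ATC flag, and a C09D record is still correctly positive for taking one class or the other.

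A reader might also infer that ACEi combinations are certainly the group left without a flag. Read literally, the SAP assigns them C09D, so they receive both flags. The no-flag outcome needs a dictionary fact that the documents do not give. On the documents alone the fault is symmetric. The pairing of C09C with C09D for ARBs suggests that the ACEi row is the wrong one, but does not prove it.

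Finally, the fault is a single letter in text read from a PDF, and the eGFR formula shortly before it is visibly garbled. A misread letter cannot be excluded, though the four rows are otherwise complete and their descriptions differ. The printed table should be looked at first.

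**Conclusion.** The point holds as a minor coding-table error. SAP Table 2, applied as written, cannot place any C09D product in one class, and the visible text gives no way round it. The consequence is confined to the derived ARB-versus-ACEi classification and whatever listing, summary or subgroup draws on it. The primary result does not change.

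The number of subjects affected cannot be stated. A reader might want a count such as 6 to 18 subjects, which is 10% to 30% of 60. That share is purely an assumption, and the count would merge two groups that may be affected in different ways. Nor can one say that every combination user is misclassified for every purpose, because the either-class answer remains right for any C09D record.

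The conclusion rests on two assumptions: that the table was read correctly from the PDF, and that programming follows the SAP's rule of selecting by code alone.

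**What to change.** 1. Confirm the printed Table 2. Then look up the 3rd-level codes for ARB combinations and for ACEi combinations in the WHO Drug version named in SAP 5.1.
2. Correct the faulty C09D cell so that each code maps to one class. The ACEi row is the likelier one to change, but the dictionary decides.
3. Before database lock, check that every randomized subject has at least one of the two flags and that any subject with both really takes both classes. Resolve exceptions against the coded drug names.
4. Where an output or subgroup uses the split, state that it is derived from Table 2.

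The cost is one table cell, one line of code and one data check. No analysis needs to be redesigned.
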